16.7 Pass/fail criterion to be applied to the results of the clinical investigation

The pass/fail criterion for the clinical investigation is whether using the active device per protocol results in a higher percentage of absence of moderate or severe pain at two hours compared to the sham device.

16.8 Analysis sets

16.8.1 Intention-to-treat (ITT) analysis set

The ITT includes all study attacks from all participants who underwent randomization and who reported headache score at the two-hour time point in at least one study attack. The ITT analysis set will not exclude attacks with protocol deviations or use of rescue medication before the two-hour time point. The ITT data set will be used for analysis of the primary and secondary effectiveness end points.

If any subjects in the ITT population have a missing headache score at the two-hour time point, multiple imputation will be used to impute their headache score for the analysis of primary and secondary endpoints, as described in the Statistical Analysis Plan.

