13.10.6 Use of rescue medication

The participants will via ePRO be prompted to answer whether they have used rescue medication, at the time points two, twenty-four and forty-eight hours after the initiation of treatment.

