16.4 Analysis of Secondary Effectiveness Endpoints

To support potential device labelling claims, key secondary end points will be analyzed according to a fixed-sequence step-down procedure. The ITT analysis set will be used for hypothesis tests for the secondary endpoints.

The end point analysis will be performed by an independent evaluator who is blinded to the type of intervention (active/sham) assigned to each of the two Stage 1 treatment groups.

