#### 1.6 Analysis sets

#### 1.6.1 Intention-to-treat (ITT) analysis set

The ITT includes all study attacks from all participants who underwent randomization and who reported at least one study attack. The ITT analysis set will not exclude attacks with protocol deviations or use of rescue medication before the two-hour time point. The ITT data set will be used for analysis of the primary and secondary effectiveness end points.

If any subjects in the ITT population have a missing headache score at the two-hour time point, multiple imputation may be used to impute their headache score for the analysis of primary and secondary endpoints, as described in section 1.9.

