| Categorical      | 
 
Headache Score at 2 hours (HS2)
 
Most Bothersome Symptom Score at 2 hours (MBS2)
 
Functional Disability Score at 2 hours (FDS2)
 
Participant Satisfaction at 48 hours (PS48)
 
Light Sensitivity Score at 2 hours (LSS2)
 
Nausea Score at 2 hours (NS2)
 
Sound Sensitivity Score at 2 hours (SSS2)
 
 | Ordinal logistic regression using the
proportional odds model with device type
(active or sham) as the exposure variable.
Threshold p value: 0.05   |

Table 3: Hypothesis testing for primary and secondary endpoints

The following Stage 2 exploratory endpoints will be compared to corresponding baseline values reported at Site Visit 1:

- How many times in the past month has the participant taken respectively a prescription acute migraine drug or an over-the-counter acute analgesic, with the intention to treat migraine.
- Proportion of patients who used an opioid drug to treat migraine the past month
- Proportion of patients who have been hospitalized for migraine in the past month

All hypothesis tests will be performed on the ITT data set of attacks. In the resulting data set each attack will constitute a data point and each patient will constitute a cluster including from one to three data points. The statistical analysis will take clustering into account by using the adjusted  $\chi^2$  statistic for clustered binary data developed by Donner and Banting (Donner and Banting, 1988) and validated by others (Gonen et al., 2001; Jung et al., 2001). This method negates the risk of type I errors that is incurred if clustering is disregarded. In the event that changes are made to the statistical analysis plan, these changes will be submitted for approval to the Competent Authorities.

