# 1.9 Sensitivity Analysis for Missing Data

All attempts will be made to minimize missing data and to ensure the primary endpoint is powered such that an analysis of complete data will be considered the primary analysis for the study.

A sensitivity analysis of the primary effectiveness endpoint will be conducted as a tipping-point analysis, to examine the impact of missing data. It will only be conducted if the hypothesis test passes (i.e., rejects H0). We will start by assuming that all missing primary effectiveness endpoints have values indicating the inferiority of Rehaler (i.e. all subjects missing data in the treatment group did not have AMSP2 and all subjects missing the primary endpoint in the control group did have AMSP2). If the primary effectiveness hypothesis is not passed, we will change one missing endpoint until the hypothesis test passes. This will enable determination of the amount of missing data that would alter the final result on the primary effectiveness endpoint.

If any study attacks in the ITT population have missing outcomes at 2 hours and: 1) the missingness is due to the patient's study condition or treatment (missing for cause) or 2) the analysis is underpowered using complete data (observed proportion of missingness is greater than assumed), five (5) multiple imputations will be used for the primary effectiveness endpoint. This consists of imputing values for each missing value as a set, analyzing the results for each set, and then pooling the results. The primary effectiveness endpoint is binary, so the imputation method will be a multiple logistic regression.

In addition, an analysis will be conducted in which if the hypothesis test of the primary effectiveness endpoint does not pass, the hypothesis test will be repeated using the per-protocol analysis population. This test is for sponsor's information only, and will not be used to support the study objective.

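### The protocol's ITT set requires an observed two-hour headache score and the SAP's does not; the two definitions need to be aligned

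*Protocol*

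**What the plan says.** The entry conditions differ:

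- **Protocol 16.8.1:** randomised participants "who reported headache score at the two-hour time point in at least one study attack".
- **SAP 1.6.1:** "all participants who underwent randomization and who reported at least one study attack".

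The two paragraphs are otherwise almost the same. Both keep attacks with protocol deviations or early rescue use, and both assign the set to the primary and secondary effectiveness endpoints. Protocol 16.4 repeats this: "The ITT analysis set will be used for hypothesis tests for the secondary endpoints". SAP 1.7.3 says "All hypothesis tests will be performed on the ITT data set of attacks".

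Both documents also make the ITT set the population for imputation. In the protocol, "multiple imputation will be used to impute their headache score for the analysis of primary and secondary endpoints"; in the SAP, "multiple imputation may be used to impute their headache score for the analysis of primary and secondary endpoints". SAP 1.9 adds that "an analysis of complete data will be considered the primary analysis for the study", sets two conditions for imputing, and plans a tipping-point analysis. The protocol plans no tipping-point analysis.

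Some outcomes are collected after two hours. Protocol 13.10.6 prompts for rescue medication "at the time points two, twenty-four and forty-eight hours after the initiation of treatment", and Protocol 13.10.8 collects satisfaction at 48 hours.

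Protocol section 16 presents itself as a summary of the SAP. Neither document has a precedence rule, and the SAP change log lists no change to the ITT definition.

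**The concern.** The protocol's condition selects participants on whether the primary outcome was observed. Someone who reported study attacks but missed every two-hour entry is in the SAP's set and outside the protocol's. Three consequences follow.

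1. **PS48** is collected on a separate, later form, so such a participant may have a usable value that only the SAP's set would count.
2. **Rescue use from 2 to 24 hours (Res24)** may be exposed in the same way, if it can be derived from the 24-hour form alone.
3. **Multiple imputation** under the protocol's set would never reach participants with no two-hour score. One of the SAP's triggers for imputation is missingness caused by the patient's condition or treatment, so these participants may be informative.

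PS48 and Res24 both belong to the fixed sequence that supports labelling claims. Their denominators should not be open to choice once the data are seen.

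**Working it through.** **Inputs (SAP 1.5.1 and Table 1).** 200 randomised; 22% drop out; 10% of attacks lack two-hour data; one third of participants each have 1, 2 and 3 study attacks, so the mean is 2.

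**The plan's own figure.** 200 × (1 − 0.22 − 0.10) = 136, which matches Table 1. This sum treats 10% of attacks as 10% of randomised subjects (20 people). Below, the 10% is applied to attacks, as the SAP's sentence states it.

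**Reporting participants.** If the 22% are those with no reported study attack, which is how SAP Appendix 2.1 defines dropout, then 200 × 0.78 = 156 participants report 156 × 2 = 312 study attacks. Of these, 312 × 0.10 = 31.2 lack a two-hour score.

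**Case A: misses independent between attacks.** With m attacks, the probability that all are missing is 0.1^m. The expected number of missing attacks belonging to such a participant is m × 0.1^m.

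| Attacks m | P(all missing) | Missing attacks in such participants |
|---|---|---|
| 1 | 0.100 | 0.100 |
| 2 | 0.010 | 0.020 |
| 3 | 0.001 | 0.003 |
| Mean over thirds | 0.111/3 = 0.037 | 0.123/3 = 0.041 |

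- Participants in the SAP's set but not the protocol's: 156 × 0.037 = 5.8, about 6.
- Their missing attacks: 156 × 0.041 = 6.4, which is 6.4/31.2 = 20.5% of all missing two-hour outcomes. The protocol's set keeps 31.2 − 6.4 = 24.8.

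**Case B: misses fully clustered within participants (assumption).**

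- Participants who differ: 156 × 0.10 = 15.6, about 16.
- All 31.2 missing outcomes then lie outside the protocol's set.

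**At N=240.** 240 × 0.78 = 187.2 reporters, of whom 187.2 × 0.037 = 6.9 (case A) to 187.2 × 0.10 = 18.7 (case B) differ.

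**PS48.** Only those who also completed a 48-hour form change its denominator, and the documents give no figure for that share. If the share is between 0 and 1, the difference at N=200 is 0 to about 6 participants in case A and 0 to about 16 in case B. In attacks, the upper limits are 6.4/312 = 2.1% and 31.2/312 = 10%.

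**Endpoints that do not change on observed data.** A participant with no two-hour form adds no observed value to AMSP2, PF2, MBSF2, HS2, MBS2, FDS2, LSS2, NS2 or SSS2. This takes the two-hour items as missing together. SPF24 and FR48 both require pain freedom at two hours, so neither can be shown to be met without that score.

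**The case against.** The strongest reply is that the protocol defers to the SAP. Section 16 calls itself a summary, the SAP already holds the better definition, and an analyst working from the SAP would use it. The SAP's primary analysis is on complete data, so the main result cannot move. Res24 and PS48 are seventh and eighth of the twelve secondary endpoints and are tested only if the primary and every earlier secondary test reject. Most of this stands, and it keeps the point minor. It does not remove the point: a summary that adds an entry condition is inconsistent with what it summarises, and no precedence rule settles the matter.

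Four stronger readings are tempting, and the documents do not support them.

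- **That the two documents run different tipping-point analyses, or that the planned one will look too robust.** Only SAP 1.9 plans one, and the SAP's own ITT set keeps participants with no two-hour score. A worst-case start on the protocol's set (24.8 missing outcomes in case A, none in case B) is an analysis that neither document plans.
- **That Res24 certainly differs.** It covers rescue use only after two hours. Protocol 13.10.6 does not say whether the 24-hour question separates use before and after that point, and the case report form content is not part of these documents. Without the two-hour form, Res24 may not be derivable.
- **That the 0.486 intraclass correlation measures how missed forms cluster.** The SAP gives it for the device's preliminary data, as an input to the clustered test of response. Nothing links it to missingness, so only the two bounding cases are shown above.
- **That imputed results would shift materially.** SAP imputation is conditional, and under a missing-at-random model participants with no observed two-hour outcome add little information. No change in any estimate has been shown.

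**Conclusion.** The inconsistency is real and current. The protocol's definition makes ITT membership depend on the outcome being observed. It excludes participants who have PS48 (and Res24, if derivable) but no two-hour score, and it removes them from any imputation. The SAP's definition fits the rest of the plan better: its Appendix 2.1 counts participants who reported a study attack before leaving as contributing to the endpoint analysis.

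At N=200 the two sets differ by about 6 of 156 reporting participants with independent misses, and by up to about 16 with full clustering. These counts rest on the SAP's 22%, 10% and equal-thirds assumptions, and on the clustering pattern, which the documents do not give. They are upper limits for PS48 in each case. No effect on a PS48 or Res24 estimate, p-value or power has been calculated. The observed-data primary result is unchanged. The separate question of when imputation applies (the protocol says it will be used, the SAP that it may be) does not bear on this point.

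**What to change.** In Protocol 16.8.1, replace the entry condition with the SAP 1.6.1 definition: all randomised participants who reported at least one study attack, whether or not a two-hour headache score was given. Add that the secondary endpoints (including Res24 and PS48), any multiple imputation and the SAP's tipping-point analysis all use this set. The SAP's exploratory set, which is built on the ITT set, then follows without further change.

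The cost is a sentence or two in the protocol, handled through the modification procedure in Protocol 20.2. It needs no extra data, visits or participants, and should be done before treatment groups are unblinded for the final analysis.

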16.8.2 As-treated analysis set

The as-treated analysis set includes all participants who received a study device, whether or not it was the actual randomized device. Subjects will be grouped by the device they actually used. This analysis set will be used for assessment of safety.

16.8.3 Per-protocol analysis set

The per-protocol analysis set includes all study attacks with a reported headache score at the twohour time point, in which:

- The participant started using the study device within five minutes of the beginning of aura and before development of moderate or severe pain
- The participant did not use rescue drugs before the two-hour assessment point
- There were no changes in concomitant preventive treatment during the study that might potentially affect response.

• There were no other major protocol deviations

When comparing the ITT and Per Protocol analysis sets, the impact of protocol deviations and user errors can be investigated with the aim of identifying potential improvements to the investigational device and instructions for use. The ITT analysis set will also be used to analyse the impact of protocol deviations on the outcome parameters (e.g. use of rescue medication during the first two hours and starting the use of the device after the onset of headache).

16.9 Handling of Missing Data

All attempts will be made to minimize missing data. However, if any subjects in the ITT population have missing primary endpoints, five (5) multiple imputations will be used for the analyses. This consists of imputing values for each missing value as a set, analyzing the results for each set, and then pooling the results. The primary effectiveness endpoint is binary, so the imputation method will be a multiple logistic regression.

17 Data capture and management

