### 1.5 Power and sample size calculation

#### 1.5.1 Assumptions

The estimated study size of 200 to 240 included participants has been determined on the basis of data from the pilot study (Fuglsang et al., 2018) and post-market data collected in Denmark, Sweden and Germany from 2018 to 2020.

To estimate the sample size for this trial, it was assumed that 12% of subjects in the sham group and 30% of subjects in the active group would experience PF2. For AMSP2, a 26% response rate in the sham group and a 61% response rate in the active group was assumed.

The primary statistical test for this analysis will be a  $\chi^2$  significance test adjusted for clustered data (using the methods of Donner and Banting (Donner and Banting, 1988)) since subjects could contribute more than one migraine attack. The intraclass correlation coefficient (ICC) from preliminary data on this device was 0.486. This is a group-sequential design with one interim analysis, so the O'Brien Fleming Spending function will be used to set significant thresholds of 0.0052 at the interim analysis and 0.048 at the final analysis.

Power and sample sizes were estimated via simulation using the above parameters for a  $\chi^2$  significance test adjusted for clustered data. These simulations assumed a third of subjects would have one migraine attack during the course of the study, a third of subjects would have two study attacks, and a third of subjects would have three study attacks. In the interim analysis, a more refined method of estimating number of attacks per participant will be employed, using the observed attack frequencies from the interim data (cf. section 1.4). Additionally, it was expected that 22% of subjects would drop out of the trial and 10% of attacks would have missing data at the 2 hour time point, for a total of 32% of randomized subjects that would not provide data usable for the statistical analysis of the primary or secondary endpoint.

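### Five imputations with no stated seed leave a borderline result partly dependent on the random seed; at the planned AMSP2 effect the verdict is practically unaffected

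*Protocol*

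**What the plan says.** Both documents fix the number of imputations at five but apply it under different conditions.

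- Protocol 16.9 imputes whenever an ITT subject lacks the primary endpoint: "five (5) multiple imputations will be used for the analyses". Protocol 16.8.1 extends imputation to the secondary endpoints.
- SAP 1.9 states that "an analysis of complete data will be considered the primary analysis for the study". It imputes on either of two triggers: "the missingness is due to the patient's study condition or treatment (missing for cause", or "the analysis is underpowered using complete data (observed proportion of missingness is greater than assumed". In those cases "five (5) multiple imputations will be used for the primary effectiveness endpoint". SAP 1.6.1 makes imputation optional for primary and secondary endpoints, where Protocol 16.8.1 makes it mandatory.
- On the model, SAP 1.9 says only that "the imputation method will be a multiple logistic regression". Neither document gives a seed, the covariates, the handling of several attacks from one patient, or how the adjusted chi-square results are pooled.
- The final threshold for AMSP2 and PF2 is p = 0.048 (SAP 1.4 and 1.7.3). Testing is fixed-sequence, so one failure stops every later labelling claim.

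**The concern.** The usual defence of five imputations is that the estimate loses little efficiency. The p value is more sensitive. With five imputations the between-imputation variance is estimated on 4 degrees of freedom, and the pooled estimate itself shifts from seed to seed. When the result is compared with a fixed cut-off, the same trial data can pass under one seed and fail under another. With no seed in the plan, the documents also cannot show that only one run was made. Because of the fixed sequence, a chance failure at AMSP2 or PF2 would close off the endpoints below it.

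**Working it through.** **1. Reproduce the plan's power.** Inputs from SAP 1.5: "For AMSP2, a 26% response rate in the sham group and a 61% response rate in the active group was assumed"; "The intraclass correlation coefficient (ICC) from preliminary data on this device was 0.486"; one, two or three attacks per subject in equal thirds; 136 usable subjects of 200; alpha 0.048 two-sided (z = 1.977).

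- Design effect = (1 + 2 × 1.486 + 3 × 1.972)/6 = 1.648.
- Attacks per arm = 68 × 2 = 136. Effective number = 136/1.648 = 82.5.
- Null SE = √(2 × 0.435 × 0.565/82.5) = 0.0772. Alternative SE = √((0.61 × 0.39 + 0.26 × 0.74)/82.5) = 0.0722.
- Power = Φ((0.35 − 1.977 × 0.0772)/0.0722) = Φ(2.73) = 99.7%, against 99.1% stated.

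The same formula for PF2 gives 81.1%. Simulation gives 82% to 88% depending on how clustered data are generated, against 85.5% stated. The plan's inputs are therefore a usable base.

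**2. How often two seeds disagree over whole trials.** Simulated trials had 156 subjects (200 less 22% dropout), one to three attacks each, ICC 0.486 and attacks missing at random. Imputation was logistic on arm with parameter draws, followed by Rubin pooling of the difference in proportions with design-effect variance. Each of 120 to 300 datasets per scenario was re-imputed under 100 seeds. If a fraction f of seeds is significant, two seeds disagree with probability 2f(1 − f).

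| AMSP2, active vs sham (five imputations) | 10% missing | 15% | 20% | 30% |
|---|---|---|---|---|
| 61% vs 26% (planned) | 0.02% | 0.2% | 0.1% | 1.2% |
| 46% vs 26% (complete-case power about 80%) | 2% | 5% | 7% | 9% |
| 40% vs 26% (complete-case power about 50%) | 5% | 7% | 11% | 12% |

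With 50 imputations, the 46% vs 26% figure at 15% missing falls to 1.6–1.9%. At the planned effect, disagreement with five imputations reaches 12% only when 60% of attacks are missing.

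**3. Relate missing attacks to the fraction of missing information (FMI).** Information per subject = (E m)²/E[m + m(m − 1)ρ], where m is the number of observed attacks.

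- Complete data: 2²/(2 + 0.486 × 2.667) = 4/3.296 = 1.214.
- 10% missing: 1.8²/(1.8 + 0.486 × 0.81 × 2.667) = 3.24/2.850 = 1.137.
- FMI = 1 − 1.137/1.214 = 0.063.

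On the same basis, FMI 0.10 needs about 15% missing attacks and FMI 0.20 about 29%.

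**4. A borderline result.** Assume z = 2.2, which is p = 0.028 with unlimited imputations. Set total variance 1 and between-imputation variance B = FMI. For M imputations, draw the pooled estimate from N(2.2, B/M) and b from B·χ²(M − 1)/(M − 1). Then T = 1 − B + (1 + 1/M)b, referred to t with Rubin's degrees of freedom (200,000 draws).

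| FMI | Seeds missing 0.048, M = 5 | Two seeds disagree, M = 5 | Seeds missing, M = 50 |
|---|---|---|---|
| 0.06 | 5% | 9% | about 0% |
| 0.10 | 13% | 22% | about 0% |
| 0.20 | 27% | 40% | at most about 0.3% |

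**5. PF2, if five imputations are used there too.** Take 85.5% as the power with unlimited imputations, so mean z = 1.977 + 1.058 = 3.035, and apply step 4 to z drawn around that mean.

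| FMI | Disagree, M = 5 | Disagree, M = 50 | Power lost, M = 5 |
|---|---|---|---|
| 0.06 | 3% | 1% | 0.5 points |
| 0.10 | 4.5% | 1.3% | 1 point |
| 0.20 | 8% | 2% | 2.5 points |

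**6. How many imputations.** For datasets with complete-case p between 0.03 and 0.07 and 15% missing, the median SD of p across seeds is 0.017, 0.011, 0.007, 0.0045 and 0.003 for M = 5, 10, 20, 50 and 100. Two seeds disagree in 37%, 27%, 19%, 13% and 9% of pairs.

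**The case against.** A reader might infer that whenever the SAP calls for imputation, the primary verdict hangs on the seed. The documents do not support that. The two SAP triggers concern why and how much data are missing, not how close p is to 0.048. Under the SAP, complete data are otherwise the primary analysis and involve no random draws. At the planned effect, stated power is 99.1% and step 2 finds almost no disagreement.

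The large percentages in step 4 are also conditional on a chosen borderline z. With five imputations and FMI 0.10, the miss rate falls to about 0.5% at z = 2.5 and to practically nothing at z = 3. FMI 0.20 corresponds to nearly three times the assumed 10% of missing attacks. The SAP also plans a tipping-point analysis when the primary test passes, which examines fragility to missing data without random draws. Fifty is partly a judgement: in step 4, 20 imputations already bring the miss rate to 0.4% at FMI 0.10.

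All of this stands, and it limits the point to borderline results. What remains is that such results can occur, at AMSP2 if the effect is smaller than planned and at PF2 even under the planning assumptions, and that the protection costs almost nothing.

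**Conclusion.** The point holds for a result near the threshold and is minor. If AMSP2 behaves as planned, the choice of five imputations will almost never change the verdict. At 46% against 26%, two seeds would disagree in roughly one trial in 50 to one in 11 over 10% to 30% missing attacks. For PF2 the range is about 3% to 8%, but only if the five-imputation rule is applied there: SAP 1.9 specifies it for the primary endpoint alone, while Protocol 16.8.1 and SAP 1.6.1 extend imputation to secondary endpoints.

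Assumptions not in the documents are missingness at random, the imputation model, Rubin pooling of the difference, attacks rather than individuals as the variance denominator, the reduced effects, the missing rates above 10%, and the FMI values. Pooling the chi-square statistics instead gave similar results at 15% missing (0.03% at the planned effect and 6% at 46% vs 26%). Simulation error is about 1 to 3 points on the scenario averages in step 2 and larger for subsets near the threshold.

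**What to change.** In Protocol 16.9 and SAP 1.9, replace five with at least 50 imputations and pre-specify the random seed. In the same edit, state the imputation model (including how a patient's other attacks enter it) and the pooling rule for the adjusted test, and reconcile the differing conditions for imputation in the two documents.

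The essential change is one number and one seed in each document, with negligible computing time. It has two limits. More imputations shrink seed dependence but do not remove it exactly at the threshold, where the fixed seed at least makes the result reproducible. Neither step corrects bias from data missing for cause.
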